## **5 STATISTICS AND METHODOLOGY**

### **5.1. Statistical analysis plan and sample size calculation**

Statistical analyses will be performed by Dr. med. [name], MSci in biostatistics (Heidelberg University/Germany). [name] performed the sample size calculation. Sample size calculation and statistical analyses will be performed using the R statistical software.

#### Sample size calculation

Sample size calculation was performed in a separate simulation study using the total reimbursement divided by the length of hospital stay for the surgical department of the Kantonsspital St. Gallen in 2018. Sample size estimation was based on a two-sided significance level of  $\alpha = 0.05$  and a power of 90%. The increase in reimbursement was assumed to be 5% in the intervention group. Furthermore, in 15% of patients a shortening of the length of stay by one day was assumed in the intervention group. Randomization was 1:1. A drop-out rate of 10% was assumed. Based on this assumptions, a total of 1200 patients (600 per group) would be needed

to prove a significant increase in the total reimbursement divided by the length of hospital stay. According to the case load in 2018, the recruitment period would last 6 months.

#### Statistical analysis plan

The primary endpoint total reimbursement divided by the length of hospital stay will be analysed by a nonparametric Mann-Whitney U-test. For the secondary endpoints Length of hospital stay, total reimbursement per case, and Case mix index the Mann-Whitney U-test will be applied too. For the secondary endpoint severity of complications both a Mann-Whitney U-test and a Chi-Square test will be applied. For the secondary endpoint rehospitalisation rate, a Chi-Square test will be applied. Auxiliary multivariable analyses for continuous outcomes will be performed using the mean ranks.

No interim analysis and no multiple testing is planned.

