## 1 STUDY SYNOPSIS

Sponsor / Sponsor-Investigator	Name(s) and contact details of Sponsor / Sponsor-Investigator
Study Title	Impact of Semi-automated proposal and optimization of diagnoses and surgical procedures for precoding: a randomized controlled trial
Short Title / Study ID	Semi-automated Precoding
Protocol Version and Date	Version 2 (dated 24/05/2019)
Study Registration	Intended: https://clinicaltrials.gov/
Study Category and Rationale	Not applicable
Background and Rationale	In a DRG system, insufficient or incorrect coding negatively impacts reimbursement. Assuming the DRG system in use to be optimal, the quality and efficacy of treatment could be improved if reporting and demission are electronically controlled and adjusted to the DRG system in use. In the long term, a fair reimbursement might reduce the pressure on the staffing ratio and thus increase the patient safety.
Risk / Benefit Assessment	The participants are not exposed to any intervention. A more accurate reporting and a treatment more adherent to the pre-setting of the DRG system in use by specially trained physicians should not impose any risk to the participants.
Objective(s) and Endpoint(s)	
Primary endpoint:
 
 
• Total reimbursement per day of hospital stay
 
 
Secondary endpoints:
 
 
• Length of hospital stay
 
• Total reimbursement per case
 
• Case mix index
 
• Severity of perioperative complications
 
• Readmission rate (safety endpoint)
 

Study Design	monocentric, randomized two-arm un-blinded study
Statistical Considerations	Continuous data are analysed using non-parametric Mann-Whitney U-tests because of skewed distributions of the data. Categorical data will be analysed using Chi-square-statistics.
Inclusion- / Exclusion Criteria	All inpatients hospitalized at the department of surgery undergoing any surgical procedure not eligible for ambulant operation at the Kantonsspital St. Gallen are included. No exclusion of vulnerable patients is planned.
Number of Participants with Rationale	According to a simulation study, a total of 1200 patients and 600 patients per arm are needed to detect an increase of 5% in the reimbursement per day of hospital stay with a power of 90%.

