## 3 STUDY OBJECTIVES AND DESIGN

### 3.1 Hypothesis and primary objective

The hypothesis of present study is that the daily monitoring and optimization of DRG coding is associated with higher reimbursement. Therefore, the primary objective is to determine if the daily monitoring and optimization of DRG coding of individual cases leads to better proceeds per day.

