## 3.2 Primary and secondary endpoints

### Primary endpoint

The primary endpoint is defined as the total reimbursement divided by the length of hospital stay including the entry and the demission day. Reimbursement per day was defined as the primary endpoint because it better reflects the ratio of costs and reimbursement in contrast to simple total reimbursement. When analysing the reimbursement in 2018, the distribution of total reimbursement per patient was extremely skewed. Hence, to achieve a reasonable power for statistical significance a high number of study participants would be needed.

The total reimbursement according to the DRG coding of each included patient will be provided by the financial department. At the end of the study the financial department will provide the total reimbursement for all included patients. The length of hospital stay of each patient will be extracted from the clinical database of the surgical department which is updated and monitored on a daily base. In cases of readmission within 18 days because of a related diagnosis the cases are aggregated.

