## 3.4. Study intervention

First, based on the randomisation list, for all patients randomized into the group with daily monitoring and optimization of DRG coding (treatment group), dedicated physicians control if all relevant diagnoses and procedures are correctly coded in the operation management software. If necessary, additional codable diagnoses and procedures are discussed with the operating surgeon and if appropriate the coding is changed accordingly. Finally, the internal coherence of the coding and the wording of the operation report are crosschecked. Therefore, the electronic signature procedure of operation reports will be adopted such that the report will not be sent before one of the dedicated physicians approved its final version.

Second, the dedicated physicians control if relevant diagnoses and procedures are correctly recorded in the drafts of the discharge reports. Therefore, patients in the treatment group are visited daily. In addition, the patient records are inspected and their relevance for the DRG coding is assessed. If necessary, relevant diagnoses are incorporated in the draft of the discharge report. Additionally, the matching between diagnoses and procedures listed in the discharge report is crosschecked. The optimal time of discharge of each patient is evaluated on a daily base.

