To support the process described above, for all patients randomized into the group with daily monitoring and optimization of DRG coding (treatment group), a pdf file with the current DRG grouping according to the procedures and diagnoses routinely coded in the Operation management software is created. Based on these procedures and diagnoses, the current DRG grouping status is estimated. Based on the estimated DRG grouping status, the actual length of stay is compared with the lower and upper limit and the mean length of stay determined by the associated actual DRG group. Additionally, based on routinely and systematically collected data in the clinical database of the surgical department, potential secondary diagnoses relevant for reimbursement are generated by computerized algorithms. For each potential secondary diagnosis, the hypothetical DRG Grouping considering the already coded procedures and diagnoses is estimated. The possible secondary diagnoses are deducted from laboratory measurements, from the extended Charlson comorbidity score routinely evaluated preoperatively by the department of anaesthesiology, and from the recording of perioperative complications.

Third, final discharge reports of patients randomized into the group with daily monitoring and optimization of DRG coding (treatment group), are controlled to ascertain the completeness of diagnoses and procedures and their concordance. Therefore, the electronic signature procedure of discharge reports will be adopted such that the report will not be sent before one of the dedicated physicians approved its final version.

In patients randomized into the control group none of the above described intervention steps will be performed. In these patients, the actual clinical routine will apply.

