## 4 STUDY POPULATION AND STUDY PROCEDURES

### 4.1 Inclusion and exclusion criteria, justification of study population

All patients undergoing any elective or emergency surgical procedure not eligible for ambulant operation at the Kantonsspital St. Gallen, Department of Surgery are eligible for study. All patients screened for the trial are documented in the screening log. Patients meeting the inclusion criteria are enrolled in the trial.

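### The primary rank test is valid, but it leaves prognostic data fixed before allocation unused and gives no effect estimate; adjust it for a short frozen covariate list and report an interval

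*Combined protocol and SAP*

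**What the plan says.** Section 5.1 (Statistical analysis plan) fixes the primary analysis: "The primary endpoint total reimbursement divided by the length of hospital stay will be analysed by a nonparametric Mann-Whitney U-test". The synopsis gives the reason: "Continuous data are analysed using non-parametric Mann-Whitney U-tests because of skewed distributions of the data". Neither place, nor any other, names a point estimate or a confidence interval. The only adjusted analysis is one sentence in section 5.1: "Auxiliary multivariable analyses for continuous outcomes will be performed using the mean ranks". It lists no covariates and no model.

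The population in section 4.1 is broad: "All patients undergoing any elective or emergency surgical procedure not eligible for ambulant operation". Section 5.3 sets 1:1 allocation in random blocks of 4, 6 and 8 and names no strata.

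Some prognostic data exist before allocation. Under sections 4.2 and 5.3, operations are imported into the departmental database daily, and one script both screens and randomises, so the triggering operation is already known. Section 3.4 mentions an "extended Charlson comorbidity score routinely evaluated preoperatively by the department of anaesthesiology". On the stay, section 3.2 says: "The length of hospital stay of each patient will be extracted from the clinical database of the surgical department". The days from admission to operation should therefore be derivable, though the plan does not say so. Age and urgency are not described as stored fields.

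**The concern.** There are two linked gaps.

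**Size of effect.** Section 3.1 says that "the primary objective is to determine if the daily monitoring and optimization of DRG coding of individual cases leads to better proceeds per day", and the trial is sized on an assumed gain. A Mann-Whitney p-value says whether the arms differ, not by how much, so the result could not be set against that gain.

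**Precision.** In such a mixed surgical population, much of the variation in reimbursement per day may come from which operation was done on whom. The primary test leaves all of that in the noise. The auxiliary model would use it, but with no named covariates, in an un-blinded study, it can be chosen after results are seen. There is also a specific hazard. In the treatment arm, "additional codable diagnoses and procedures are discussed with the operating surgeon and if appropriate the coding is changed accordingly". A model using final codes would therefore adjust for part of what the intervention does.

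**Working it through.** **Inputs from the plan.** Section 5.1: two-sided alpha 0.05, power 90%, 600 per group, 10% drop-out, 5% more reimbursement, and one day less in 15% of intervention patients.

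**The plan's own figure.** The 1200 comes from a separate simulation on 2018 data that is not in the documents, so it can be neither reproduced nor refuted. Only the drop-out step can be checked: 600 × 0.90 = 540 analysed per arm, reading 600 as already inflated.

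**Effect at 90% power on the rank scale.** Let P be the probability that a treated patient has the higher reimbursement per day.
- SE(P) = √[(2n+1)/(12n²)] = √[1081/(12 × 540 × 540)] = 0.01758
- P = 0.5 + (1.96 + 1.2815) × 0.01758 = 0.557
- 95% half-width = 1.96 × 0.01758 = 0.0344

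**Gain from adjustment.** R² is the share of rank variance explained by the covariates. It is not in the documents, so a range is assumed. Power = Φ(3.2415/√(1−R²) − 1.96); half-width = 0.0344 × √(1−R²).

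| Assumed R² | Power | Half-width |
|---|---|---|
| 0 | 90.0% | 0.0344 |
| 0.1 | 92.7% | 0.0327 |
| 0.3 | 97.2% | 0.0288 |
| 0.5 | 99.6% | 0.0244 |

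A simulation (5000 runs per setting, 540 per arm, normal errors on the log scale, one covariate, R² set on that scale) gave Mann-Whitney against adjusted ranks: 89.3% vs 92.0% at 0.1, 90.2% vs 96.9% at 0.3, and 89.7% vs 99.3% at 0.5. Type I error stayed near 5% for both.

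**Cost if the covariates explain nothing.** With k parameters spent, power ≈ Φ(3.2415 × √(1−k/1080) − 1.96):
- k = 18: 89.5%
- k = 100: 87.0%
- k = 200: 83.3%

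Simulation agrees. With 15 procedure groups, two further covariates and a missing indicator, power was 89.7% against 90.5% for Mann-Whitney. With 100 and 200 uninformative levels it was 87.3% and 82.8% against 89.8%. The level counts are assumptions.

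**Missing covariates.** At R² 0.1, with the covariate missing in 10%, 20% or 30% of patients, dropping those patients gave 89.6%, 86.4% or 83.0% power. A missing indicator gave 92.0%, 92.2% or 93.0%.

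**Codes edited after allocation.** Suppose a 4-level code (R² 0.3) is moved up one level in 5%, 10% or 20% of treated patients and the edited code is used. The estimate of P falls from 0.557 to 0.551, 0.546 or 0.536. With no true effect, the test rejects in 5.8%, 9.7% or 29.6% of trials.

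**What an interval would show.** At 90% power, the expected 95% interval for the ratio of reimbursement per day is exp[ln(ratio) × (1 ± 1.96/3.2415)].
- The synopsis puts the 5% on reimbursement per day. Ratio 1.05: exp(0.0488 ± 0.0295) = 1.02 to 1.08.
- Section 5.1 puts 5% on reimbursement and adds the shorter stay. The log ratio is about ln 1.05 + 0.15 × ln[L/(L−1)] for a typical stay of L days. Assuming L = 5 or 7, it is 0.0823 or 0.0719, a ratio of 1.09 or 1.07. Taking 1.08: exp(0.0770 ± 0.0465) = 1.03 to 1.13.

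**The case against.** The strongest reply is that nothing is broken. The test is valid under 1:1 randomisation, it leaves the analyst no choice, and 90% power is already planned. The interval could be added in one sentence without touching the primary test, and the auxiliary model cannot change the primary conclusion. All of this stands. It is why the point is an improvement, and why the interval and the covariate list are worth adopting even if the sponsor declines to change the primary test.

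The second reply is that the gain rests on an R² the documents do not give. That also stands. In simulations of section 5.1's combined effect, adjusted ranks beat Mann-Whitney in all 18 settings tried, by 3 to 14 points. But every setting gave the covariates a rank R² above about 0.1, so the gain was built in. The endpoint is a ratio, and a covariate that raises both reimbursement and stay may partly cancel.

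The third reply is that adjustment can cost power, since the plan covers any inpatient procedure and names no grouping. This stands for a procedure variable used as imported. Besides the losses shown above, a category with a single patient has leverage 1, and the HC3 standard error is then undefined. It does not stand for a capped grouping.

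**Conclusion.** The point holds as an inexpensive improvement. The primary test ignores prognostic data fixed before allocation in a very mixed, unstratified population, and the plan provides no estimate or interval.

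The missing estimate needs no assumption to establish. The power gain is conditional: about 3, 7 or nearly 10 points at an assumed rank R² of 0.1, 0.3 or 0.5, with 540 analysed per arm and 90% power as the base. The downside is about 1 point with coarse procedure groups.

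A reader might infer that Mann-Whitney is the wrong test here, or that the trial is underpowered. The documents support neither. Randomisation makes the unadjusted comparison valid, skewness is a sound reason for ranks, and 1200 can be neither confirmed nor refuted. Nor may one infer that every useful covariate is available: the preoperative score is called routine but is not stated for every patient, and the other fields need checking.

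**What to change.** **Primary test.** Regress the ranks of reimbursement per day on arm plus a short covariate list, all frozen at screening:
- the preoperative Charlson score;
- the procedure of the triggering operation, in about 15 or fewer pre-specified groups with rare procedures pooled;
- days from admission to operation, if a database check confirms that it can be retrieved;
- age and elective or emergency status, only if confirmed as stored before the SAP is final.

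**Details to settle in advance.** Name one robust standard error (for example HC3) and one missing-covariate method (a missing indicator), so that the complete-case rule in section 5.2 drops nobody for a missing covariate. Use no codes, diagnoses or complications recorded after allocation. Keep the unadjusted Mann-Whitney test as supportive. Do not switch to a log-scale model: at R² 0.1 its simulated power was 76.6% to 88.8% under skewed or heavy-tailed errors, below Mann-Whitney.

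**Estimates.** Report the adjusted probability of superiority, 0.5 + (arm coefficient / number analysed), with its 95% interval. The formula holds because the difference in mean ranks equals N × (P − 0.5). As a supportive estimate, report the unadjusted Hodges-Lehmann ratio (shift on the log scale, back-transformed) with its 95% interval. Before reading either against the target, reconcile the synopsis with section 5.1 on what the 5% applies to.

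**Cost.** SAP wording, a stored copy of the procedure code and Charlson score at screening, a check that the fields exist, and agreement on the procedure groups. The 2018 data could be used to define those groups and to show the likely R². No extra patients are needed.

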### Secondary endpoints

1. Length of hospital stay: The number of days of the hospital stay including the entry and the demission day will be extracted from the clinical database of the surgical department
2. Total reimbursement per case: At the end of the study a list of included patients will be sent to the financial department. Based on this list, the financial department will provide the total reimbursement per case measured in Swiss Francs.
3. Case mix index: At the end of the study a list of included patients will be sent to the financial department. Based on this list, the financial department will provide the effective cost weight of each patient.
4. Severity of perioperative complications: The severity of perioperative complications are already routinely recorded applying the Clavien-Dindo-Classification. This standardized classification is chosen to ascertain external and internal comparability. Perioperative complications of all operated patients are routinely recorded by a dedicated physician and stored in the clinical database of the surgical department.
5. Readmission rate: On a daily basis, all admissions and readmissions are routinely presented and discussed during the morning meeting of the surgical clinic. The list of readmissions will be cross checked with the randomisation list and the demission of the included patients.

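### The case mix index is tested only by ranking individual cost weights, so nothing planned estimates the mean cost weight that the index ordinarily denotes (minor, secondary endpoint)

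*Combined protocol and SAP*

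**What the plan says.** Section 3.2 (Secondary endpoints, item 3) lists the case mix index and describes its data in one phrase: "the financial department will provide the effective cost weight of each patient". It gives no averaging step, no definition of the index and no summary to be reported per arm.

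Section 5.1 (Statistical analysis plan) assigns the test: "For the secondary endpoints Length of hospital stay, total reimbursement per case, and Case mix index the Mann-Whitney U-test will be applied too". The synopsis gives the reason for rank tests in general: "Continuous data are analysed using non-parametric Mann-Whitney U-tests because of skewed distributions of the data". The only further analysis named for such outcomes is also rank-based: "Auxiliary multivariable analyses for continuous outcomes will be performed using the mean ranks". For the index, the plan names no difference or ratio of means and no confidence interval.

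**The concern.** In ordinary use a case mix index is one number for a group of cases, the mean of their cost weights. With one value per arm there is nothing to rank, so the Mann-Whitney test must run on the individual cost weights. It then asks whether a randomly chosen intervention case tends to carry a higher weight than a randomly chosen control case. That is a legitimate question, but it is not whether the mean weight rose.

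The intervention works case by case. Section 3.4 has dedicated physicians add or correct codes where needed, and the supporting software estimates the grouping that would follow from each candidate secondary diagnosis. Some cases may jump to another group while others stay put, which is a setting in which a mean and a rank comparison need not move together. The stake is the report: a rank-test p-value could be printed beside the words *case mix index* and read as a statement about the mean.

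**Working it through.** **What the documents give.** No effect size, power or distribution is stated for the index. The sample size, 1200 in total, is for the primary endpoint. It comes from a simulation on 2018 hospital data whose distribution is not shown, so it cannot be reproduced. The inputs used below are:

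- Two-sided alpha 0.05 (section 5.1: "Sample size estimation was based on a two-sided significance level of" 0.05) and equal allocation ("Randomization was 1:1").
- 600 per arm and 10% drop-out (section 5.1), so 600 × 0.90 = 540 evaluable per arm.
- A 5% rise, borrowed from the primary endpoint ("The increase in reimbursement was assumed to be 5% in the intervention group"), as a reference size for the index.
- **Assumed:** lognormal cost weights with log-SD 0.8 to 1.1. The documents contain no cost-weight distribution.

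**Rank-test scale.** Let θ be the probability that an intervention case outranks a control case. With n = 540 per arm, SE(θ) = √[(2n+1)/(12n²)] = √[1081/3,499,200] = 0.0176. Approximate power is Φ(d/SE − 1.96) + Φ(−d/SE − 1.96), where d = θ − 0.5.

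**Case A: uniform 5% rise.** d = Φ(ln 1.05/(σ√2)) − 0.5. This is 0.0172 at σ = 0.8 (power 16%) and 0.0125 at σ = 1.1 (power 11%). A simulated Welch test of means rejects in about 13% to 14% and 8% of trials. The two comparisons agree.

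**Case B: a random 5% of cases doubled.** The index again rises 5%. d = 0.05 × [Φ(ln 2/(σ√2)) − 0.5], which is 0.0115 (power 10%) and 0.0086 (power 8%). Welch rejects in about 13% and 8%. Allowing about a percentage point for simulation error, both tests lie between about 7% and 17% in cases A and B.

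**Case C: the costliest 5% doubled.**

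- Under the lognormal, these cases hold a share Φ(σ − 1.645) of the total weight: Φ(−0.845) = 0.199 at σ = 0.8 and Φ(−0.545) = 0.293 at σ = 1.1. Doubling them raises the index by 20% and 29%.
- A case already in the top 5% outranks, on average, 97.5% of controls, so at most 2.5 points are left to gain. Hence d ≤ 0.05 × 0.025 = 0.00125, or 0.07 standard errors. This bound needs no lognormal assumption and holds however large the uplift.
- Rank-test power is therefore about 5%, its alpha. Simulation gives θ = 0.501 and rejection in about 5% of trials. Welch rejects in about 64% (σ = 0.8) and 55% (σ = 1.1).

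**Precision of a mean-based estimate.** SE of the log ratio of means is about √[2(e^(σ²) − 1)/540]: √[2 × 0.897/540] = 0.058 at σ = 0.8 and √[2 × 2.353/540] = 0.093 at σ = 1.1. A 95% interval therefore multiplies and divides the ratio by about e^(1.96 × 0.058) = 1.12 and e^(1.96 × 0.093) = 1.20. Around a true ratio of 1.05 that is roughly 0.94 to 1.18, or 0.87 to 1.26.

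**The case against.** The best defence is that item 3 of the secondary endpoints already describes a patient-level variable. Read with it, section 5.1 tests exactly that variable, and only the label is loose. The rank test was also chosen for a stated reason, skewness, and ranking against averaging is a familiar trade-off for such data. Both arguments stand as far as they go: the Mann-Whitney test is a valid test of individual cost weights and need not be removed. They do not supply an estimate of the index, which the plan names as an endpoint in the synopsis, the secondary objectives and section 3.2.

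Three stronger readings are tempting, and the documents do not support them.

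- **That a mean-based test would rescue a modest rise.** It would not. In cases A and B Welch does about as well as Mann-Whitney, and neither has useful power.
- **That the rank result will contradict the index in this trial.** Opposite directions can be produced on paper, for instance by doubling the costliest 5% and lowering all others by 12%. Likewise, a near-flat index with a fairly sensitive rank test follows if 97% of cases gain 10% and the costliest 3% lose half. Section 3.4 describes no mechanism for lowering most cases or halving the heaviest.
- **That regrouping will be concentrated in the costliest cases.** Section 3.4 makes case-by-case change plausible, but does not say where in the distribution it will fall. Case C shows what can happen and is not a forecast.

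**Conclusion.** The point holds as a mismatch between label and analysis. The planned test addresses the ordering of individual cost weights, and nothing planned estimates or tests the arm's mean. That the index is a mean rests on the ordinary meaning of the term.

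Under a roughly uniform shift little is lost. If change is concentrated in a few heavy cases, the index could rise by some 20% to 29% while the rank test stays at its alpha level. Those percentages depend on the assumed lognormal weights and on doubling the costliest 5%; the near-zero rank-test response to any uplift confined to that group does not. The 2018 cost-weight distribution is not given, so the size of any divergence here is unknown. This is a minor point on one of five secondary endpoints.

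**What to change.** In section 5.1, state that the case mix index will be reported per arm as the mean effective cost weight, with the between-arm difference and ratio and a bootstrap 95% interval for each. Keep the Mann-Whitney test on the individual weights and label its result *effective cost weight per case*. A matching definition of the index belongs in item 3 of the secondary endpoints in section 3.2.

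The cost is a sentence or two in the plan and a few lines of R, with no new data. The downside is that the interval will be wide with skewed weights, as the precision figures above indicate, and it may well include no change even if the index rose by 5%. Replacing the rank test outright is not needed and would set aside the plan's own reason for choosing it.
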